4. SUBJECT SELECTION

The criteria for inclusion and exclusion are defined below:

4.1. Inclusion Criteria

1. Male and female subjects at least 12 years of age
2. Presence of clinical signs and/or symptoms consistent with an acute illness compatible with EV/RV infection (each of the following is required):
 - a. Presence of moderate or severe rhinorrhea defined as “attempting to relieve nasal symptoms by blowing, wiping, or sniffing at least twice per hour for any one hour within 12 hours preceding study entry,” AND
 - b. Presence of cough, sore throat or nasal obstruction.

3. Negative rapid influenza diagnostic test (required only if the subject has an oral temperature >100°F in the clinic or if the latest CDC weekly influenza report shows influenza prevalence “Regional” or higher for the institution’s state). A result from a rapid influenza diagnostic test performed on the same day that informed consent is obtained will be sufficient to meet this criterion if documentation of test results is available as part of medical history.
4. Onset of illness no more than 40 hours before enrollment in the trial. Onset of illness is defined as the first time at which the subject experienced rhinorrhea, cough, sore throat or nasal obstruction.
5. Willing and able to provide written informed consent (including assent by legal guardian if under 18 years of age) and comply with the requirements of the protocol, including completion of the subject diary

4.2. Exclusion Criteria

1. Persons requiring or anticipated to require in-hospital care
2. Cystic fibrosis
3. Cardiac arrhythmia
4. Immunologic disorders or receiving immunosuppressive therapy (e.g., for organ or bone marrow transplants, immunomodulatory therapies for certain autoimmune diseases)
5. Untreated HIV infection or treated HIV infection with a CD4 count below 350 cells/mm³ in the last 6 months
6. Persons with sickle cell anemia or other hemoglobinopathies
7. Poorly controlled insulin-dependent diabetes mellitus (HbA1C >8.0%)
8. Concurrent infection at the screening examination that requires systemic antimicrobial therapy
9. Females of childbearing potential who are either pregnant or sexually active without the use of birth control. Female subjects of child-bearing potential that are sexually active must have a negative baseline pregnancy test and must agree to continue an acceptable method of birth control for the duration of the study and for 1 month post-treatment. A double barrier method, oral birth control pills administered for at least 2 monthly cycles prior to study drug administration, an IUD, or medroxyprogesterone acetate administered intramuscularly for a minimum of one month prior to study drug administration are acceptable methods of birth control for inclusion into the study. Female subjects are considered of childbearing potential unless they are postmenopausal (absence of menstrual bleeding for 1 year - or 6 months if laboratory confirmation of hormonal status), or have had a hysterectomy, bilateral tubal ligation or bilateral oophorectomy.
10. Females who are breastfeeding
11. Receipt of any dose of NTZ within 30 days prior to screening
12. Prior treatment with any investigational drug therapy within 30 days prior to screening

13. Subjects with active respiratory allergies or subjects expected to require anti-allergy medications during the study period for respiratory allergies
14. Known sensitivity to NTZ or any of the excipients comprising the NTZ tablets
15. Subjects unable to take oral medications
16. Subjects who, in the judgment of the Investigator, will be unlikely to comply with the requirements of this protocol including completion of the subject diary

5. STUDY PROCEDURES

5.1. Screening Evaluation (day 1)

Before screening, subjects and their parents/guardian(s) will be informed of the nature of study, and written consent must be obtained prior to participation. After giving informed consent, the subject will be assigned a subject number, and the following procedures will be carried out:

1. Complete medical history.
2. Full physical examination including body weight and vital signs (blood pressure, pulse, respiratory rate and oral temperature using standard electronic oral thermometer provided by Sponsor).
3. Collection of demographic information and smoking history.
4. Urine pregnancy test for all females of childbearing potential.
5. Recording of time of onset of respiratory symptoms.
6. Evaluation according to eligibility ([inclusion](#) and [exclusion](#)) criteria.

5.2. Baseline (day 1, same day as screening evaluation)

At baseline, the following procedures will be carried out:

1. Collection of two nasopharyngeal swabs (one from each nostril) using nylon flocked dry swabs (Copan Diagnostics) for RT-PCR and culture.
2. Collection of blood sample for laboratory safety tests.
3. Collection of a urine sample for routine urinalysis (glucose, protein and blood).
4. Review and recording of any concomitant medications.
5. Provision of an electronic diary to subject via his/her own smartphone or a provisioned device, and subject completion of baseline electronic diary under supervision and instruction of study site personnel, including the Practice Diary, FLU-PRO Questionnaire, Activity Diary, and Study Drug Intake and Temperature Diary.
6. Randomization and dispensing of study medication (medication assigned in sequential order).

7. Administration of the first dose of study medication with food (< 1 hour after food intake) under observation of Investigator or a member of Investigator's staff, and entry in Study Drug Intake and Temperature Diary.
8. Instruct subject regarding:
 - a. *Administration of study medication.* Subjects will be instructed to take the study medication (two tablets) twice daily with food (< 1 hour after food intake, preferably a high-fat meal but at a minimum a cereal bar). The subject should take his/her second dose as close as possible to 12 hours after the first dose. Then he/she will take the study medication every 12 hours for the remaining 4 days.
 - b. *Completion of subject diary.* Subjects will be instructed on completion of the electronic diary.
 - c. *Use of birth control.* Female subjects of childbearing potential, if sexually active, will be instructed to continue an acceptable method of birth control for the duration of the study and for 1 month post-treatment. Acceptable methods of birth control include a double barrier method, oral birth control pills, an IUD, or medroxyprogesterone acetate administered intramuscularly.
 - d. *Follow-up visits:* Subjects will be instructed to return to the clinic for follow-up on Day 7 and Day 22.
 - e. *Seeking emergency care or contacting the study physician or nurse:* Subjects must be informed to seek emergency medical care or contact the study physician or nurse if they develop any of the following symptoms listed below during the full 22-day study and follow-up period.

CALL 911 (United States) OR LOCAL EMERGENCY SERVICES (outside of United States) OR HOSPITAL OR CONTACT STUDY PHYSICIAN, IF:

- Trouble breathing including shortness of breath
- Severe headache, stiff neck, confusion or excessive somnolence

CALL STUDY NURSE OR PHYSICIAN, IF:

- Extremely high fever >104°F (40°C)
- Fever ($\geq 100.4^{\circ}\text{F}$ or $\geq 38^{\circ}\text{C}$) lasts for longer than 3 days
- Increased difficulty breathing
- Wheezing develops
- New pain develops or pain localizes to one area, such as an ear, the throat, the chest, or the sinuses
- Symptoms become more severe or frequent
- Fever ($\geq 100.4^{\circ}\text{F}$ or $\geq 38^{\circ}\text{C}$) returns after being absent for 24 hours
- Symptoms recur or any difficulty breathing following 5-10 days resolution of illness
- An allergic-like reaction occurs or is suspected
- Abnormal behavior

9. Review and record adverse events

5.3. Day 2 – Day 22

A study physician, nurse or other site personnel will review each subject's electronic diary entries daily to ensure compliance with collection of diary data. If a subject has not completed his/her diary or if errors are suspected, the study personnel will contact the subject to implement appropriate corrective actions.

5.4. Day 2-5 Telephone Monitoring

A study physician, nurse or other site personnel will make daily telephone calls to subjects on each of Days 2, 3, 4 and 5 of dosing to screen for potential complications and review adverse events. Subjects will be referred for immediate care as needed based on the screening. All information gained from telephone monitoring will be included in the EDC system for each subject. [Note: In lieu of a telephone call, this information may be obtained during the Day 2 and 3 home or office visits (see below).]

5.5. Day 2 and 3 Evaluations

A study physician, nurse or other study personnel will visit each subject at home (or at the clinic or another location as agreed with the subject) on each of Days 2 and 3 to (i) collect two nasopharyngeal swabs for detecting and quantifying EV/RV, and (ii) screen for potential complications and adverse events. Subjects will be referred for immediate care as needed based on the screening. All information gained from these visits will be included in the case report forms for each subject. In addition, a blood sample for pharmacokinetics will be collected on Day 3. The Day 2 and Day 3 visits will occur at approximately the same time of day that the patient took his/her first dose of study medication (approximately 24 and 48 hours after the first dose). On Day 3, the blood sample for pharmacokinetics will be collected before the first dose of that day.

Study sites or subjects may opt out of these Day 2 and Day 3 visits due to site staffing, subject availability or other practical considerations or preferences; nevertheless at least 75% of subjects enrolled in the trial are expected to complete the Day 2 and Day 3 visits and related procedures (for viral kinetics and pharmacokinetics).

5.6. Day 7 Follow-up (± 1 day)

Subjects will return to the clinic on Day 7, and the following procedures will be performed:

1. Brief physical examination (body weight and vital signs with nursing physical assessment) including symptom directed physician physical examination as required by subject symptoms. Vital signs will include blood pressure, pulse, respiratory rate and oral temperature (use standard electronic oral thermometer provided by Sponsor).
2. Collection of two nasopharyngeal swabs using nylon flocked dry swabs (Copan Diagnostics) for RT-PCR and culture.
3. Collection of blood sample for laboratory safety tests.
4. Collection of urine sample for routine urinalysis.
5. Review of compliance with study medication, collection of medication bottle with any unused medications, and completion of the pill count log form.

6. Review and recording of concomitant medications.
7. Review and recording of adverse events/side effects and complications.

5.7. Day 22 Follow-up (+3 days)

Subjects will return to the clinic on Day 22, and the following procedures will be performed:

1. Brief physical examination (body weight and vital signs with nursing physical assessment) including symptom directed physician physical examination as required by subject symptoms. Vital signs will include blood pressure, pulse, respiratory rate and oral temperature (use standard electronic oral thermometer provided by Sponsor).
2. Collection of two nasopharyngeal swabs using nylon flocked dry swabs (Copan Diagnostics) for RT-PCR and culture (to be tested for presence of virus only if the sample collected at the preceding time point had detectable virus).
3. Review and recording of concomitant medications.
4. Review and recording of adverse events/side effects and complications. Note that all adverse events and complications must be followed until their resolution or stabilization even beyond the 22-day study period.

5.8. Unscheduled Visit

Subjects returning to the clinic for an unscheduled visit due to worsening symptoms or adverse events will be evaluated at the discretion of the Investigator as is medically warranted. Tests and/ or procedures performed at this visit may include, but are not limited to, the following:

1. Brief physical examination (body weight and vital signs with nursing physical assessment) including symptom directed physician physical examination as required by subject symptoms. Vital signs will include blood pressure, pulse, respiratory rate and oral temperature (use standard electronic oral thermometer provided by Sponsor).
2. Collection of two nasopharyngeal swabs using nylon flocked dry swabs (Copan Diagnostics) for RT-PCR and culture.
3. Collection of blood sample for laboratory safety tests.
4. Collection of urine sample for routine urinalysis.
5. Review of compliance with study medication.
6. Review and recording of concomitant medications.
7. Review and recording of adverse events/side effects.

5.9. Study Discontinuation

Rules for discontinuation of a subject or for discontinuing the study are provided in section [11.2](#). All subjects discontinued from the study before Day 7 will be evaluated at study discontinuation using the procedures described above for Day 7. All subjects discontinued from the study after Day 7 will be evaluated at study discontinuation using the procedures described above for Day 22.

5.10. Electronic Subject Diary

Electronic subject diaries will be completed twice daily through Day 21. The electronic diaries will capture the following information:

1. Medication intake (twice daily at time of medication intake).
2. Oral temperature (twice daily at time of medication intake). Use standard electronic oral thermometer provided by Sponsor.
3. Use of other medications taken by the subject not previously captured in the subject's medication history. Document in detail including dose in milligrams or other applicable units, time of ingestion, and the reason for use of the medication (at time of medication intake).
4. FLU-PRO Questionnaire (once daily between 7 pm and 11 pm) to characterize symptoms.
5. Activity assessment using an 11-point visual analog scale (0= unable to perform normal activity, 10= fully able to perform normal activity) (once daily between 7 pm and 11 pm).
6. Adverse experiences (once daily between 7 pm and 11 pm).

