⁶ Laboratory safety tests include hemoglobin, hematocrit, complete blood count (total and differential), platelet count, random blood sugar, total cholesterol, HDL, LDL, triglycerides, albumin, AST, ALT, GGT, alkaline phosphatase, bilirubin (total/direct), BUN, creatinine, sodium, potassium, chloride and routine urinalysis (glucose, proteins and blood).

⁷ All subjects will maintain an electronic diary until day 22 (+3). Site staff will contact subjects as needed during study to ensure timely completion of electronic diary.

⁸ Collection of unused IMP and completion of pill count log form will be performed at unscheduled visit if applicable.

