A nurse or other study personnel will visit each subject (or the subject will return to the clinic) on study Days 2 and 3 to collect two nasopharyngeal swabs, to review patient diaries, and to review symptoms and screen for complications of colds. A blood sample for pharmacokinetics will also be collected prior to the first dose of study medication on study Day 3. These Day 2 and 3 visits will occur at approximately the same time of day that the subject took his/her first dose of study medication (roughly 24 and 48 hours post-first dose). The nasopharyngeal swabs will be used to evaluate quantitative changes in viral shedding. The blood sample will be used to evaluate relationships between pharmacokinetics and virologic or clinical response. Study sites or subjects may opt out of the Day 2 and Day 3 visits due to site staffing, patient availability or other practical considerations or preferences; nevertheless, at least 75% of subjects enrolled in the trial are expected to complete the Day 2 and Day 3 visits and related procedures (for viral kinetics and pharmacokinetics).

A study physician, nurse or other site personnel will make daily telephone calls to subjects for the first five days of dosing to review symptoms and screen for complications of colds. [Note: In lieu of a telephone call, this information may be obtained during the Day 2 or 3 office or home visits (see the preceding paragraph).]

Subjects will return to the clinic on Days 7 and 22 for post-treatment follow-up, including two nasopharyngeal swabs, drug accountability, and reporting of adverse events and complications of cold. Blood and urine samples for laboratory safety tests will be collected

[figure not shown]
at Day 7. Subjects will maintain the electronic patient diaries through study Day 21. Any visits that do not occur on the prescribed date, or within 1 day of that date in the case of the Day 7 visit or within 3 days after in the case of the Day 22 visit will be recorded as protocol deviations.

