#### **11.2.2. Analysis of the Primary Efficacy Parameter**

The primary efficacy parameter, time to Symptom Response, will be derived as follows:

Event: Time of Symptom Response – time of the first dose

Censored: Time of last symptom assessment – time of the first dose

If Symptom Response is achieved at the time of the first symptom assessment diary record, the subject will be excluded from the analysis.

If Symptom Response is not achieved prior to a subject’s last available diary assessment, but the criteria are met at the last available diary assessment with no evidence of symptom relief medication intake during that diary period, time of Symptom Response will be considered to have occurred at the start of the last daily diary period.

Time to Symptom Response for the NTZ treatment group will be compared to that of the placebo treatment group using a Gehan-Wilcoxon test stratified by (1) time from onset of illness to time of first dose of study medication (0-24, >24-≤36, or >36 hours from onset), (2) pre-enrollment use of symptom relief medication, and (3) presence of underlying lung condition including asthma, COPD, or past or present history of smoking. The comparison will be graphically depicted using Kaplan-Meier curves.

Analysis Population(s): ITTI

Derived Variables: Event: Time of Symptom Response – time of first dose

Censored: Time of last symptom assessment – time of first dose

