### 11.3. Sensitivity Analyses of the Primary Efficacy Analysis

#### 11.3.1. Sensitivity Analysis Assuming Time of Symptom Response of 21 Days for Discontinued Subjects

Repeat the primary efficacy analysis assuming a time of Symptom Response of 21 days (504 hours from first dose of study medication) for subjects who discontinued the study prior to achieving Symptom Response.

Analysis Population(s): ITTI

Derived Variables: See [Section 11.2: Primary Efficacy Analysis](#)

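### The diary ends on Day 21 in the text but on Day 22 (+3) in the schedule footnotes, and the SAP sets no cut-off; under the footnotes, the 504 h assigned to dropouts is not a worst case

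*Protocol*

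**What the plan says.** **End of the diary.** Protocol 5.10: "Electronic subject diaries will be completed twice daily through Day 21". SAP 8.2: "Subjects will maintain the electronic patient diaries through study Day 21". Footnote 7 of the protocol schedule (Table 13) says otherwise: "All subjects will maintain an electronic diary until day 22 (+3" days), and footnote 7 of the SAP schedule (Table 17) has the same sentence. Protocol 5.3 also has site staff reviewing diary entries from Day 2 to Day 22.

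**Follow-up window.** The primary objective covers 21 days. The sample-size sections of both documents censor at day 21, labelled hour 504.

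**Derivation.** SAP 11.2.2 has "Censored: Time of last symptom assessment – time of the first dose" and gives no latest day or hour. If the response criteria are first met at the last available diary, the response is dated to the start of that diary period, 24 h before the entry, with no second diary needed. SAP 11.4.1, for normal activities, likewise has no maximum time.

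**Sensitivity analysis.** SAP 11.3.1 repeats the primary analysis assuming "a time of Symptom Response of 21 days (504 hours from first dose of study medication) for subjects who discontinued the study" before responding.

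**The concern.** Each document gives two end dates for the diary that carries the primary endpoint, and no analysis rule settles which applies. Under the footnote, the length of observation depends on when the final visit is booked.

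The consequence falls on SAP 11.3.1, the only sensitivity analysis aimed at early loss. Giving dropouts a late response time is unfavourable to them only if that time follows everything actually observed. If completers are still under observation at 504 h, an event at 504 h counts as a response that those completers had not achieved.

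A second gap is separate from the end date. The 504 h rule is triggered by discontinuing the study, not by loss of diary data. A non-responder who stops the diary on Day 6 but attends Day 22 stays censored at Day 6. Neither of the other two sensitivity analyses (per protocol, and excluding chromaturia) is designed for such subjects.

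**Working it through.** **Inputs**
- Day numbering: Day 1 is the day of first dose. Protocol 5.5 places the Day 2 and 3 visits "approximately 24 and 48 hours after the first dose", so Day d is nominally 24 × (d − 1) h.
- Diary clock time, Protocol 5.10: "FLU-PRO Questionnaire (once daily between 7 pm and 11 pm".
- First dose between 8 am and 5 pm: an assumption, since the documents give no clinic hours.

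**The plan's own figure.** 21 × 24 = 504 h, as stated.

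**Diary times.** Time of the Day d diary = 24 × (d − 1) + (diary clock time − first-dose clock time). The clock difference runs from 19 − 17 = 2 h to 23 − 8 = 15 h. The latest possible response under the last-diary rule is that time minus 24 h.

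| Last diary | Latest censoring (h) | Latest response (h) | Against 504 h |
|---|---|---|---|
| Day 21 | 480 + 2 to 480 + 15 = 482-495 | 458-471 | both earlier |
| Day 22 | 504 + 2 to 504 + 15 = 506-519 | 482-495 | censoring later |
| Day 23 | 528 + 2 to 528 + 15 = 530-543 | 506-519 | both later |
| Day 25 | 576 + 2 to 576 + 15 = 578-591 | 554-567 | both later |

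The Day 21 row does not depend on the assumed clinic hours: 504 h is Day 22 at the clock time of the first dose, so any Day 21 evening diary precedes it. A Day 22 evening diary follows 504 h whenever the first dose was given before 7 pm.

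Under the footnote, maximum follow-up differs between subjects by up to 3 × 24 = 72 h. True responses can be dated up to 567 − 504 = 63 h after the assigned value.

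**Size of the effect.** An illustrative unstratified Gehan-Wilcoxon simulation used 1,500 trials of 300 per arm.
- Placebo times were log-logistic with the 302 h median of Protocol Table 7 and its ratio of upper to lower quartile (643/135).
- NTZ times were scaled to a median of 302 − 48 = 254 h.
- First doses were spread over 8 am to 6 pm, and dropout times over 24-480 h.
- Positive z favours NTZ. The last-rank column places dropouts after all observed times.

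| Dropout, placebo / NTZ | Last diary | Primary, mean z | Dropouts at 504 h | Dropouts at last rank |
|---|---|---|---|---|
| 12% / 12% | Day 21 | 1.665 | 1.647 | 1.647 |
| 12% / 12% | Day 22 | 1.668 | 1.661 | 1.649 |
| 12% / 12% | Day 22-25 | 1.673 | 1.666 | 1.652 |
| 6% / 18% | Day 21 | 1.662 | 1.169 | 1.169 |
| 6% / 18% | Day 22 | 1.665 | 1.629 | 1.149 |
| 6% / 18% | Day 22-25 | 1.670 | 1.613 | 1.123 |

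With a Day 21 end, 504 h and last rank are identical. With later ends, about 160-166 of 600 subjects are observed beyond 504 h, and about 7 respond after it when last diaries are spread over Days 22-25. On average about 41 of 600 subjects discontinue before responding and receive the assigned value. With unequal dropout the 504 h analysis then stays close to the primary result (1.63 against 1.67) and no longer tests it.

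**The case against.** The strongest reply is that this is a stray footnote. The body text of both documents says Day 21, the objective says 21 days, and the footnote in the SAP repeats the protocol's. On the Day 21 reading, 504 h equals the stated follow-up, matches the sample-size censoring time and is a proper worst case. All of that stands. A reader might infer that 504 h is wrong because no evening diary falls on it; the documents do not support that.

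A reader might also infer that the primary result is compromised by uneven follow-up. Uneven follow-up arises only under the footnote. The final visit is booked under double-blinding, which gives no evident route to imbalance between arms, and the simulated primary z moves by about 0.01.

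Two further inferences go too far. The sample-size text allows for up to 12% incomplete data, 0.12 × 600 = 72 subjects, but SAP 11.3.1 applies only to those who discontinue before responding, so 72 is not the number re-ranked. And the Table 13 heading reads Day 22±3, against "5.7. Day 22 Follow-up (+3 days" days) in the protocol text. That sign may be a PDF reading error, because the SAP copy prints +3 and Table 13's own footnote says +3, so it warrants a check and no more.

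On diary stoppers, Protocol 5.3 has staff review entries daily and contact subjects who miss them. That should reduce the loss, but it does not say how the remainder is analysed.

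What the reply does not remove is the conflict itself. Reading the footnote as stopping short of the named day would still allow diaries to Day 24, and no SAP rule discards late records if they are collected.

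**Conclusion.** The conflict is real and in current text, and it leaves the meaning of SAP 11.3.1 undetermined. With a Day 21 end, 504 h is a valid worst case. With the footnote's end, dropouts assigned 504 h rank ahead of non-responding completers censored at 506-591 h and, for last diaries on Day 23 or later, ahead of some true responders dated as late as 567 h.

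The effect on the primary comparison is negligible. The effect on the sensitivity analysis averages about 0.01 in z with equal dropout and about 0.5 with 6% against 18%. Those unequal rates are an assumption, not a forecast. The curves and clinic hours are also assumed, and the z values are no check of the stated 90% power, whose input curves are in a figure not available here.

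The omission of non-responders who stop the diary but stay in the study holds under either end date. Its size cannot be derived from the documents. The changes are worth making because they cost almost nothing and make the one early-loss analysis do its job.

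**What to change.** 1. State one diary end day in Protocol 5.10, SAP 8.2 and footnote 7 of both schedule tables. Day 21 matches the 21-day objective. Check that the visit window in protocol Table 13 agrees with Protocol 5.7.
2. Add to SAP 11.2.2 and 11.4.1 that diary records after the Day 21 diary are not used for events or censoring.
3. In SAP 11.3.1 keep 504 h, which then lies after every observed time and remains a prespecified constant. Apply it to every ITTI subject without a Symptom Response whose last diary precedes the planned final diary, whether or not the subject formally discontinued.

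The cost is a few sentences in the SAP and the correction of two footnotes. The downside is that a few late diary records go unused.
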